3 STUDY OBJECTIVES

Our specific objectives are as follows:

1. Collaboratively design an automated alcohol brief intervention (Health4Her-Automated; H4H-A) with women who participate in breast screening and, after development, test the prototype, seek feedback, and refine the final product.
2. Examine intervention effectiveness on drinking intentions, alcohol literacy and alcohol consumption among women attending a breast screening service for routine mammography.
3. Evaluate the intervention's reach, uptake, feasibility and acceptability.

3.1 RANDOMISED CONTROLLED TRIAL OUTCOMES/HYPOTHESES

Primary outcome/hypothesis:

- a) *Change in next-month drinking intentions (primary outcome)*: we hypothesise that there will be a greater change in the extent to which participants intend to reduce the amount of alcohol they consume among intervention participants, relative to control, between baseline and immediately post-intervention (likert scale response item) (15).

Secondary outcomes / hypotheses:

- b) *Change in next-month drinking intentions*: we hypothesise that there will be a greater change in the extent to which participants intend to reduce the amount of alcohol they consume

among intervention participants, relative to control, between baseline and 4-weeks post-intervention (likert scale response item) (15).

- c) *Change in drinking intentions – standard drinks*: we hypothesise that there will be a greater reduction in the intended number of standard drinks consumed over the next month among intervention participants, relative to control, between baseline and 4-weeks (quantity/frequency response items) (16).
- d) *Proportion of participants intending to reduce alcohol consumption*: we hypothesise that there will be a greater change in the *proportion* of intervention participants, relative to control, intending to reduce their next-month alcohol consumption between baseline and immediately post-intervention (15).
- e) *Proportion of participants intending to reduce alcohol consumption*: we hypothesise that there will be a greater change in the *proportion* of intervention participants, relative to control, intending to reduce their next-month alcohol consumption between baseline and 4-weeks (15).
- f) *Change in knowledge of alcohol as a breast cancer risk factor (alcohol-breast cancer literacy)*: we hypothesise that there will be a greater change in the proportion of intervention participants accurately identifying alcohol as a risk factor for breast cancer between baseline and 4-weeks, compared to control participants.
- g) *Change in alcohol literacy*: we hypothesise that there will be a greater change in the proportion of intervention participants, relative to control participants, accurately identifying the i) the increased breast cancer risk associated with drinking one average restaurant serve of wine a day; ii) number of standard drinks in an average restaurant serve of red wine; iii) maximum number of standard drinks per week recommended by current Australian Alcohol Guidelines between baseline and 4-weeks.
- h) *Change in alcohol consumption*: among women who have had an alcohol drink in the past month, we hypothesise that there will be a greater reduction in alcohol consumption among intervention participants relative to control participants, between baseline and 4-weeks.
- i) *Change in knowledge of other breast cancer risk factors*: we hypothesise that, in both intervention and control arms, there will be a significant increase in the proportion of participants accurately identifying inactivity and excess weight as risk factors for breast cancer between baseline and 4-weeks. (This represents a potential value-add of the intervention among women in the control group, and those who do not drink alcohol).

4 STUDY DESIGN

This will be a hybrid type II effectiveness-implementation trial (17, 18) comprising a randomised controlled trial alongside a mixed-methods program evaluation, guided by applicable elements of the Reach, Effectiveness, Adoption, Implementation, and Maintenance (RE-AIM) framework, Consolidated Framework for Implementation Research (CFIR) (19, 20) and Non-adoption, Abandonment, Scale-up, Spread, and Sustainability (NASSS) framework (21).

4.1 COLLABORATIVE DESIGN OF H4H-A

Study design: We will use an iterative, qualitative participatory design to co-produce and test the H4H-A intervention and research procedures with breast screening service consumers.

Setting: Researchers conducting collaborative design focus groups will be based at Turning Point, a national addiction treatment and research centre in Melbourne, Australia. Focus groups will be conducted onsite or online.

Participants: Also utilised to inform our pilot trial, breast screening service consumers will be recruited predominantly from the Lifepool breast screening cohort (N=54,000) using systematic, purposive sampling to achieve representation of consumers from health inequity groups (e.g. rural, remote and regional consumers, CALD consumers).

Data collection and analyses: Participatory co-design prioritises collaboration with target audiences to design successful products, systems, and services (22). A series of in-person and/or online collaborative design semi-structured workshops (incorporating ideas-generating and problem-solving activities) will be held with breast screen service consumers to identify issues related to automated alcohol brief intervention offered in the breast screening setting, and define what is needed to make a successful intervention. Ideas will be generated for intervention design, trial and dissemination in practice, to create and refine the intervention prototype and, after development, test the prototype, seek feedback, and refine the final product. Workshops will be audio-recorded, and transcribed verbatim. Workshop transcriptions, observations, and interactive data will be organised using NVivo, with data analysed using deductive thematic analysis. Interim data analyses and observations will feed-forward to subsequent workshops and inform intervention creation/testing.

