We recently completed a world-first trial (N=558), funded by VicHealth and the Eastern Health Foundation, supported by Maroondah BreastScreen (trial site) and BreastScreen Victoria, and approved by the Eastern Health Human Research Ethics Committee (LR19/011/50551), to test the effectiveness of a prototype of an electronic alcohol brief intervention (Health4Her; researcher-

administered screening alcohol questions, intervention activated by the researcher for the participant to view on an iPad alone). The electronic alcohol brief intervention model was chosen to minimise disruption to service workflow and need for human resource to implement within the busy breast screening environment. In this trial, participants reported poor alcohol literacy (4 in 5 did not have knowledge of the alcohol-breast cancer link) and a desire for more information. The Health4Her intervention was found to be highly acceptable to breast screening service consumers. For the primary outcome, there were significant increases in the proportion of participants accurately identifying alcohol as a clear breast cancer risk factor from baseline to 4-weeks in intervention (OR=41.82, 95% CI=17.76, 98.49, $p<0.001$) and control (OR=4.92, 95% CI=2.75, 8.79, $p<0.001$) arms, with a significantly greater increase in the intervention arm ($p_{\text{arm} \times \text{time}} < 0.001$) (Findings are currently under peer-review for publication). BreastScreen staff were highly supportive of the Health4Her intervention as part of routine care, however, the manually delivered intervention, dependent on dedicated human resource to administer, was considered unviable to implement in practice.

As such, the overall aim of this study is to i) collaboratively design an automated alcohol brief intervention with women who participate in breast screening, ii) examine its effects on drinking intentions and alcohol consumption among women attending breast screening service for routine mammography and iii) understand the factors affecting intervention implementation using mixed-methods program evaluation.

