4.2 RANDOMISED CONTROLLED TRIAL OF H4H-A

Study design: A single site, double-blind, parallel-group randomised controlled trial, comprising baseline and 4-week follow-up assessments.

Setting and participants: This trial will aim to recruit at least 78 participants (39 per trial arm). Women attending Maroondah BreastScreen for routine mammography (throughput ~65/screening day), aged 40+ years, with or without a breast cancer history, and drinking at any level of alcohol consumption will be eligible to participate after they complete their screening appointment. **Exclusion criteria:** Women not able to read or comprehend English to enable participation, or who do not have access to computer, tablet or smartphone to complete the follow-up assessment, will be excluded from this iteration of the research. Women who are pregnant will be excluded (also an exclusion of breast screening). Women who participated in the previous Health4Her study will also be excluded (a woman can provide her name to the recruitment researcher for cross-checking against the previous participant list if she is unsure of previous participation. The same recruitment researcher that was onsite for the previous study will be onsite for this study. The researcher will exercise care to ensure security and privacy measures are used, i.e. the list will only include name and year of birth; the list

will be hosted on a secure server managed by Monash University eSolutions and accessible to only the recruiting researcher via a secure login; the list will never be shown to potential participants).

Recruitment: Maroondah BreastScreen reception staff will provide a reminder text message one day prior to recruitment days to flag the study occurring onsite (as well as serving to confirm appointment attendance). Upon arrival at Maroondah BreastScreen, the receptionist will query whether women are aware of the study and provide them with a study flyer to read while waiting for their appointment. Study posters will also be visible on the waiting room notice board and in the screening rooms. At the end of the screening appointment, the radiographer will ask whether the client would like to hear more about the study from the onsite researcher / be involved, and if the client agrees or has further questions, the radiographer will introduce the client to Researcher 1.

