5 CONSENT

5.1 PARTICIPATION IN THE COLLABORATIVE DESIGN OF H4H-A

For participation in a collaborative design workshop, researchers will provide a written (via email or post) and verbal explanation (aims, process, potential benefits and risks). Potential participants will

have the opportunity to discuss the study and ask questions. Participants will be advised that they can withdraw from the study at any time and that their decision whether to take part or not to take part, or to take part and then withdraw, will not affect their relationship with Eastern Health. The researcher will seek verbal informed consent from the individual to a) participate in the interview, and b) have their interview audio-recorded, with the understanding that the data they provide (i.e. what they say, demographic information provided) will only be used in an anonymised format (i.e. in such a way that they cannot be identified) in reports, publications and/or presentations that arise from this project.

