The randomised controlled trial component of this study necessarily requires limited disclosure including active concealment of the trial's alcohol focus. The trial will be described as the “Health4Her women’s health study” to minimise the salience of the trial’s alcohol focus, to a) increase its relevance for all women attending breast screening (so that women who drink alcohol are not singled out for participation), and to blind participants to group allocation. Participants will instead be informed that the study is concerned with promoting health across a range of lifestyle factors, which accurately corresponds to the intervention conditions (active = ~4 minutes of alcohol brief intervention plus ~3 minutes of lifestyle information; control = ~3 minutes of lifestyle information not inclusive of alcohol information) and planned outcome assessments (comprising questions about diet, exercise, and alcohol). It is anticipated that participants will not be exposed to an increased risk of harm as a result of limited disclosure/concealment; this approach was endorsed by breast screening service consumers in our recently completed preliminary study of Health4Her.

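### Women who co-designed or tested Health4Her-Automated are not excluded from its trial, so one attending the site could be randomised unblinded and already exposed

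*Combined protocol and SAP*

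**What the plan says.** Protocol section 4.1 describes workshops with breast screening service consumers that are meant "to co-produce and test the H4H-A intervention and research procedures with breast screening service consumers". The topic is open: attendees are asked to "identify issues related to automated alcohol brief intervention offered in the breast screening setting". Their ideas are then used "to create and refine the intervention prototype and, after development, test the prototype, seek feedback, and refine the final product". For consent, section 5.1 states that "researchers will provide a written (via email or post) and verbal explanation (aims, process, potential benefits and risks" will be given.

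The trial works on the opposite footing. Section 5.2 says the randomised component "necessarily requires limited disclosure including active concealment" of the alcohol focus, and gives blinding to allocation as one of the reasons. Section 4.2 calls the trial double-blind.

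Section 4.2 lists four exclusions: inability to read or comprehend English, no device for the follow-up survey, pregnancy, and earlier participation, the last worded as "Women who participated in the previous Health4Her study will also be excluded". A woman who is unsure can have her name checked against a list holding name and year of birth. Workshop attendance is not mentioned there, and the SAP addendum has no analysis rule for it.

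**The concern.** The protocol already accepts that a woman with earlier Health4Her exposure should not enter this trial. The same reasoning applies with more force to women who helped write and test the very product under trial. Section 1.2 puts the design work in the six months immediately before the trial, so their exposure is also more recent.

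Two things are at stake for any such woman. First, concealment has failed: she knows the study is about alcohol, and she would probably recognise the alcohol animation or notice that it is missing. Second, her baseline intention and knowledge may already reflect the content, so her change from baseline does not measure what the trial intends. With a target of 39 per arm, one woman is 1/39 = 2.6% of an arm.

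**Working it through.** **Does any exclusion reach these women?** The only candidate is the one for the previous study. Section 2 describes the earlier work as a finished trial: "We recently completed a world-first trial (N=558" participants). Section 4.2 ties the check to that trial's participant list and adds that "The same recruitment researcher that was onsite for the previous study will be onsite for this study". The workshops are a phase of the present study (sections 3 and 4.1), held onsite or online by researchers based elsewhere. The exclusion does not cover them.

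**Can overlap occur?** Workshop women come predominantly, but not only, from a cohort of 54,000, sampled partly for rural, remote, regional and CALD consumers. The number of workshop women and their screening sites are not stated. As a pure assumption, take 10 to 40 workshop women, each with a 0.1% to 5% chance of entering the trial:

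- Expected overlap: 10 × 0.001 = 0.01 up to 40 × 0.05 = 2 women.
- Chance of at least one: 1 − 0.999^10 = 1% up to 1 − 0.95^40 = 87%.

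The range is wide because nothing in the documents narrows it.

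**The plan's own figures.** Section 4.2 plans a change of 2.37 to 3.37 (1.00) in the active arm and 2.37 to 2.63 (0.26) in the control arm, so the planned difference is 1.00 − 0.26 = 0.74, with 39 per arm for 80% power. The pre-post correlation is not stated, so 78 can be neither confirmed nor refuted. Allowing for 5% attrition and 30% non-drinkers gives 39 × 0.95 × 0.70 = 25.9 per arm. With SDs of 1.18 and 1.22, a correlation of about 0.70 then reproduces 80% power. The same value gives about 85% at 45 per arm, as the protocol states.

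**Effect of one pre-exposed woman on the primary contrast.** Assume her change is 0.

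- Active arm: mean change = 38/39 × 1.00 = 0.974. Difference = 0.974 − 0.26 = 0.714, which is 0.026/0.74 = 3.5% lower.
- Control arm: mean change = 38/39 × 0.26 = 0.253. Difference = 1.00 − 0.253 = 0.747, which is 0.007/0.74 = 0.9% higher.
- Average under 1:1 allocation: (3.5 − 0.9)/2 = 1.3% lower, which equals 1/78.

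**Other assumptions.** If an active-arm woman changes by 0.26, as a control would, the loss is (0.74/39)/0.74 = 2.6%. If she instead reports one point more change than planned, because she is answering for a product she helped build, the difference rises by (1/39)/0.74 = 3.5%.

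**Two women, each with no change.** Both active: 37/39 × 1.00 − 0.26 = 0.689, or 6.9% lower. Both control: 1.00 − 37/39 × 0.26 = 0.753, or 1.8% higher. Expected: 2/78 = 2.6% lower.

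**Power.** At the back-solved correlation of about 0.70, shrinking 0.74 by k/78 gives about 79% for k = 1, 78% for k = 2 and 76% for k = 4, against 80% for none.

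**The case against.** The strongest reply is that the problem may be empty. To overlap, a workshop woman must screen at this one site, on a recruitment day, within a short window, and agree to take part. The source cohort is large and the sampling leans partly towards groups away from a single metropolitan service. This stands: nothing shows that any such woman enrolled. A woman who had attended a Health4Her workshop might also mention it when she sees the study name, but that is a hope and not a rule.

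A reader might infer that any such woman pulls the result towards no effect, in the control arm as an already exposed control and in the active arm for lack of room to change. The documents do not support that. The exposed-control argument fits a comparison of post-intervention values alone. The SAP compares change from baseline, and her baseline would already carry the exposure, so a control who does not move slightly widens the contrast.

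It can also be said that an exclusion line comes too late. The SAP addendum, dated 7 February 2024, describes baseline and randomisation in the past tense. For that sample the objection holds, but it does not touch the name check or the sensitivity analysis.

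**Conclusion.** The eligibility gap is real on the text: workshop and prototype-test participants know the alcohol aim, have worked with the content, and are not excluded. The consequence is minor. Under the no-change assumption the expected dilution is about 1.3% of the planned difference per woman, from 3.5% lower in the active arm to 0.9% higher in the control arm, and unblinded responding could move it either way. With an assumed 0 to 2 such women, power would stay at about 78% to 80%, given a correlation of about 0.70 that the protocol does not state.

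The documents support neither a claim that the trial's blinding failed overall nor a claim that its result is biased in a known direction. They support only that such a woman could be randomised unblinded and pre-exposed, and that nothing planned would detect it.

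**What to change.** For any remaining or later recruitment, extend the prior-participation exclusion in section 4.2 to women who took part in the collaborative design workshops or prototype testing of Health4Her-Automated, and add their names and years of birth to the existing cross-check list. As that check is offered only to a woman who is unsure, the question about earlier involvement should name the workshops.

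For women already randomised, compare workshop names with the trial list, report the number found by arm even if it is zero, and if any are found repeat the primary analysis without them as a sensitivity analysis. The SAP addendum's list of sensitivity analyses should include this.

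The cost is a negligible loss of eligible women, a minor amendment through the ethics committee under section 12.2, and one short name comparison. A reported zero would close the question.

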4.2 RANDOMISED CONTROLLED TRIAL OF H4H-A

Study design: A single site, double-blind, parallel-group randomised controlled trial, comprising baseline and 4-week follow-up assessments.

Setting and participants: This trial will aim to recruit at least 78 participants (39 per trial arm). Women attending Maroondah BreastScreen for routine mammography (throughput ~65/screening day), aged 40+ years, with or without a breast cancer history, and drinking at any level of alcohol consumption will be eligible to participate after they complete their screening appointment. **Exclusion criteria:** Women not able to read or comprehend English to enable participation, or who do not have access to computer, tablet or smartphone to complete the follow-up assessment, will be excluded from this iteration of the research. Women who are pregnant will be excluded (also an exclusion of breast screening). Women who participated in the previous Health4Her study will also be excluded (a woman can provide her name to the recruitment researcher for cross-checking against the previous participant list if she is unsure of previous participation. The same recruitment researcher that was onsite for the previous study will be onsite for this study. The researcher will exercise care to ensure security and privacy measures are used, i.e. the list will only include name and year of birth; the list

will be hosted on a secure server managed by Monash University eSolutions and accessible to only the recruiting researcher via a secure login; the list will never be shown to potential participants).

Recruitment: Maroondah BreastScreen reception staff will provide a reminder text message one day prior to recruitment days to flag the study occurring onsite (as well as serving to confirm appointment attendance). Upon arrival at Maroondah BreastScreen, the receptionist will query whether women are aware of the study and provide them with a study flyer to read while waiting for their appointment. Study posters will also be visible on the waiting room notice board and in the screening rooms. At the end of the screening appointment, the radiographer will ask whether the client would like to hear more about the study from the onsite researcher / be involved, and if the client agrees or has further questions, the radiographer will introduce the client to Researcher 1.

Randomisation, interventions and procedure: The study will be described as the “Health4Her women’s health study” to minimise the salience of the trial’s alcohol focus, and to increase its relevance for all women. In the active and control arms, participants will be provided with an iPad and earbuds, and will self-complete consent (via a landing page) and baseline assessment before being randomly assigned (1:1 allocation ratio, utilising a “permuted blocks of variable size” scheme embedded in the iPad) to receive 1) ~4 minutes of alcohol brief intervention plus ~3 minutes of lifestyle information (active arm: H4H-A), or 2) ~3 minutes of lifestyle information not inclusive of alcohol information (control arm) via interactive animation. An assessment immediately post-intervention will be completed on the iPad (comprising only the set of intention questions containing the primary outcome item). A 4-week follow-up assessment will be completed offsite via online survey, with the follow-up researcher prompting/assisting with survey completion when required.

Alcohol brief intervention (active arm): Finalised through the collaborative design process, and based on brief intervention and applied behaviour change principles, the alcohol brief intervention will include information and behaviour-change content regarding alcohol consumption such as: messaging around alcohol risks/harms, positive-framed messaging on the health benefits of reducing alcohol intake, and behaviour change strategies (e.g. drink counting, goal setting, behaviour substitution, problem solving) (12, 23-26). This iteration of the research provides an opportunity to refine and add to the evidence-based intervention elements utilised in the pilot (e.g. provide the intervention in ‘chunks’, where the participant will view 1-2 minutes of animation before completing a brief activity such as setting goals or problem solving strategies), with the goal of strengthening intervention response. **NB.** H4H-A will be aligned with the National Health and Medical Research Council’s recently revised Australian Alcohol Guidelines (i.e. no more than 10 standard drinks per week, with the message ‘the less you drink, the lower your risk of alcohol-related harm’). Post-session information will be provided via email (i.e. an electronic brochure summarising alcohol brief intervention content).

Lifestyle information (control and active arm): Finalised through the collaborative design process, potential elements will be: information on physical activity and maintaining a healthy weight, which can also reduce breast cancer risk (27, 28). Post-session information will be provided via email (i.e. an electronic brochure on nutrition for maintaining a healthy weight).

Implementation evaluation of a modified active arm: This pilot group does not form part of the planned randomised controlled trial or power and sample size calculation, but is included based on findings from the previous phase of this research. A theme from the previous program evaluation was that there may be some barriers to implementing the intervention onsite in practice, due to i) women not having time to complete the intervention onsite, and ii) there being not enough space to implement the intervention at smaller services. Therefore, a small group of women (n~20) who cannot participate on the day of screening (e.g. due to other commitments, paid parking timing out, etc. as identified in the previous study) will be offered to participate in the modified active arm *offsite*. Women who agree to take part in this element of the research will access the intervention after their appointment using their personal device (e.g. computer, iPhone, iPad) and will be offered a QR code before leaving the breast screening setting and/or sent a text/email following their appointment with the link to the Health4Her-Automated platform, to receive the participant information sheet, and complete verbal consent, baseline assessment and alcohol brief intervention. While the two-arm trial remains the main focus of this study (i.e. testing the benefits of an alcohol and lifestyle brief intervention offered to women attending breast screening, which can act as a window of opportunity to increase engagement with breast cancer risk reduction information), the addition of the modified active arm will permit evaluation of this alternative implementation approach.

Power and sample size estimate:

While this study will examine reach, uptake, feasibility and acceptability as important end-points, it will be powered to test the effectiveness of H4H-A in decreasing women's drinking intentions. The sample size has been calculated using data from a previous, related study examining the effects of alcohol warning information about the alcohol-breast cancer link on drinking intentions (15). Using a Likert 5-point response scale (1 = not at all, 5 = to a very great extent, this study showed that the warning information, *Alcohol increases your risk of breast cancer*, increased participants' intention to reduce the amount of alcohol they consume from a pre-exposure mean of 2.37 (SD = 1.18) to a post-exposure mean of 2.63 (SD = 1.22).

Given some differences in the previous study (i.e. the message about alcohol and breast cancer risk was not personally relevant to the whole sample comprising males and females 18-65 years; a single health message was provided, which is different to the Health4Her intervention containing several 'active ingredients' based on alcohol brief intervention and applied behaviour change principles), we anticipate a greater increase in participants' intention to reduce the amount of alcohol they consume in the current study. Further, based on our previous research, we anticipate some assessment reactivity among the control group.

Power and sample size estimations were conducted using General Linear Mixed Model Power and Sample Size (GLIMPSE) software. We estimate (factoring in 5% attrition, and 30% of women attending breast screening who do not drink or have not drunk in the past month) that a total sample size of at least 78 (39 per group) will have 80% power ($\alpha < 0.05$) (a total sample size of 90 [45 per group] will provide 85% power, $\alpha < 0.05$) to detect a change in women's drinking intentions of 2.37 to 3.37 (change = 1.00) in the intervention group, and a change of 2.37 to 2.63 (change = 0.26) in the control group between baseline and immediately post-intervention. Therefore, this study will aim to recruit a total

sample size of at least 78 participants. Based on the barriers to participation and implementation identified in the previous phase of this research, the current study will provide an opportunity to collect some pilot data to inform scaled up research and implementation, to provide an indicator of outcomes for participants who complete a modified version of the alcohol brief intervention offsite using their own personal device (n~20).

Statistical analyses: A full Statistical Analyses Plan will be developed prior to trial commencement. All statistical tests will be two-tailed, with the alpha level set to 0.05 and analyses conducted using the most appropriate procedures in Stata or R. All randomised participants will be included in the analyses (i.e. intention-to-treat) for primary and secondary outcomes. Analyses will examine change in outcomes over time (baseline, immediately post-intervention, 4-weeks). For intention outcomes, we will examine differences in responses according to baseline alcohol consumption risk status (i.e. drinking at a level within/exceeding current national alcohol guidelines). For alcohol outcomes, sensitivity analyses will be performed for women who a) report drinking any alcohol in the past month, and b) are identified to be drinking at a level exceeding current national guidelines for weekly and/or single day consumption. The Generalised Linear Mixed Model approach with fixed effects for treatment and time, and their interaction, and random effects for subjects and assessments within subjects, will be applied to examine the treatment effect of the intervention on all outcomes.

